### 3.2.4. Study Intervention and Comparison

Usual feeding practices in our neonatal unit include: 1) administration of enteral feeds as intermittent bolus gavage every 3 hours; 2) initiation of trophic feeds within the first 96 hours after birth with 20-25 ml/kg/d; 3) progression of enteral feeds with daily increments of 20-25 ml/kg/d usually before postnatal day 7; 4) use of donor human milk as an alternative to mother's own milk if the mother is not able to supply her own milk, and 5) addition of bovine-based products that increase protein content of human milk at approximately postnatal day 14 after full enteral nutrition is established ( $> 120$  ml/kg/d) [Figure 4].

Intervention group: Infants in the intervention group will receive expressed human milk or donor human milk on feeding day 1 (within the first 96 hours after birth). On feeding day 2, a human milk-based product that increases protein content (Prolact®, Prolacta Bioscience, Inc. City of Industry, CA) will be added to human milk. This practice will continue until standard bovine-based human milk fortifiers are ordered.

Control group: Infants in the control group will receive expressed human milk or donor human milk from feeding day 1. This practice will continue until standard bovine-based products are ordered.

### 3.2.5. Blinding/Masking

Caregivers and primary outcome evaluators will be masked. Nutrition room staff not involved in patient care will be responsible for determining participant allocation to one of the supplementation groups by opening sequentially numbered sealed envelopes, dispensing feeding syringes with the allocated human milk diet (protein-enriched or usual), and masking caregivers administering the assigned dietary intervention.

### 3.2.6. Control or Monitoring of Co-interventions

This pragmatic trial will compare protein-enriched and usual human milk diets under normal clinical circumstances with no effort to strictly control interventions other than dietary intervention. Therefore, clinical care will be conducted at the clinician's discretion.

### 3.2.7. Primary Outcome

- The primary efficacy outcome will be FFM-for-age Z-score at 36 weeks PMA. The primary microbiological outcome will be composition and diversity of the gut microbiome

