## **Study Hypothesis/Question**

The central hypothesis of the proposed work is that protein-enriched human milk diets during the first 2 weeks after birth increase fat-free mass(FFM)-for-age Z scores and promote maturation of the gut microbiome at term equivalent age in extremely preterm (EPT) infants.

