### **2.1. PRIMARY HYPOTHESIS OR QUESTION**

Protein-enriched human milk diets during the first 2 weeks after birth increase FFM-for-age Z scores at term equivalent age in extremely preterm (EPT) infants.

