### **2.2. SECONDARY HYPOTHESIS OR QUESTIONS (S) (IF APPLICABLE)**

Protein-enriched human milk diets during the first 2 weeks after birth promote maturation of the gut microbiome at term equivalent age in extremely preterm (EPT) infants.

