### **4.1. STATISTICAL ANALYSIS PLAN**

All statistical analyses will use two-tail alpha to reject null hypotheses at 0.05, using R software. Continuous variables will be summarized as means  $\pm$  standard deviations (SD) or as medians and interquartile ranges (IQRs). Categorical variable will be summarized as frequencies and proportions. Group differences will be evaluated using the T Test or Wilcoxon test for continuous variables and chi-square for categorical variables. The effect size of the primary outcome will be expressed as the mean difference with 95% confidence intervals (CIs). Risk ratios (RRs) with 95% CIs will be reported for categorical outcomes. All of the efficacy and safety outcomes of the trial will be analyzed with the intention-to-treat principle.

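### The gut microbiome is a primary outcome in the Abstract and 3.2.7 but the secondary hypothesis in 2.2, and no rule says which result decides the trial

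*Combined protocol and SAP*

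**What the plan says.** The protocol ranks the microbiome in different ways in different places.

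- **Abstract, Study Hypothesis/Question.** One central hypothesis joins the two aims: the diet will "increase fat-free mass(FFM)-for-age Z scores and promote maturation of the gut microbiome at term equivalent age".
- **2.1, primary hypothesis.** FFM only: "Protein-enriched human milk diets during the first 2 weeks after birth increase FFM-for-age Z scores at term equivalent age".
- **2.2, secondary hypothesis.** The microbiome: "Protein-enriched human milk diets during the first 2 weeks after birth promote maturation of the gut microbiome at term equivalent age".
- **Abstract (Primary Outcome) and 3.2.7.** Both outcomes stand under the primary heading: "The primary efficacy outcome will be FFM-for-age Z-score at 36 weeks PMA", followed by "The primary microbiological outcome will be composition and diversity of the gut microbiome". The secondary lists (Abstract and 3.2.8) do not contain the microbiome. No diversity index, composition test or time point is attached to it, although 3.2.11 collects stool weekly to day 28 and once before discharge.
- **4.1, Statistical Analysis Plan.** "All statistical analyses will use two-tail alpha to reject null hypotheses at 0.05". The section gives no testing order, division of alpha or multiplicity rule, and does not say whether one or both outcomes must succeed. Its microbiome power statement (about 80% for about 2-fold effects at 5%, 75 infants per arm) concerns the detection of individual taxa.
- **4.2, Sample Size.** The calculation uses FFM-for-age Z-score alone: 126 evaluable, raised to 150.

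**The concern.** A reader of 3.2.7 would conclude that the trial has two primary outcomes, the second with two parts. A reader of 2.1, 2.2 and 4.2 would conclude that it has one. The plan does not settle the matter, so the reading could be chosen once the results are known.

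Suppose FFM shows no difference and a microbiome comparison gives p < 0.05. Under 3.2.7 that could be reported as a met primary outcome, although the plan controls error only test by test. The issue does not depend on how many taxa are examined: it would remain if the microbiome were reduced to a single global test.

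**Working it through.** **1. The plan's own figure.** Inputs from 4.2: difference 0.5, SD 1, two-sided alpha 0.05, power 80%.

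n per arm = 2 × (1.960 + 0.842)² × 1² / 0.5² = 2 × 7.85 / 0.25 = 62.8, so 63 per arm and 126 in total. This matches 4.2. An exact t-test calculation gives 63.8, so 64 per arm (128 in total), which is close enough. Hypothesis 2.1 taken alone therefore has 5% error and 80% power at 126 evaluable infants. Whether 150 enrolled will yield 126 is a separate matter.

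**2. If either outcome suffices.** Each test is at 0.05 (4.1).

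- Two independent tests (FFM and one microbiome test): 1 − 0.95² = 0.0975, or 9.75%.
- Three independent tests (FFM, composition, diversity): 1 − 0.95³ = 0.1426, or 14.3%.
- Two correlated tests: 1 − P(|Z₁| < 1.96 and |Z₂| < 1.96) under a bivariate normal. The documents give no correlation, so a range is assumed:

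| Assumed correlation | Family-wise error, two tests |
|---|---|
| 0 | 9.75% |
| 0.3 | 9.5% |
| 0.5 | 9.1% |
| 0.8 | 7.8% |

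The independent-test figures are the upper end for jointly normal test statistics. Without any such assumption the ceilings are 2 × 0.05 = 10% and 3 × 0.05 = 15%. Composition and diversity come from the same stool samples, so the three-test error is likely to be below 14.3%.

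**3. If both outcomes are required.** With one test per outcome, a false joint claim needs a false rejection of at least one true null, tested at 0.05. The error of the joint claim is therefore at most 5%, and no alpha split is needed. Power is the cost:

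joint power ≤ min(power for FFM, power for the microbiome test) ≤ 80%.

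It falls below the FFM figure unless the microbiome test succeeds every time FFM does. The plan gives no power for a test of composition or diversity, so the loss cannot be computed. The 5% bound also assumes that the microbiome part is one test. If any of several unadjusted microbiome tests would do, the bound no longer holds when FFM truly differs.

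**4. If FFM is the sole primary, or is tested first in a fixed order.** Alpha stays at 0.05 and the requirement stays at 126 evaluable.

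**5. For comparison, an equal alpha split.** At 0.025 for FFM: 2 × (2.241 + 0.842)² / 0.25 = 76.04, so 77 per arm, 154 evaluable, and 154 / 0.80 = 192.5, so 193 enrolled at 20% loss. At 63 per arm, FFM power would fall to about 71%.

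**The case against.** The best defence is that the protocol uses *primary* as a label for the lead outcome within a domain. It speaks of a primary efficacy outcome and a primary microbiological outcome, and the Abstract even lists primary safety outcomes under its heading for secondary outcomes. The analysis text points to a single primary: 4.1 refers to the primary outcome in the singular and expresses its effect as a mean difference, which suits FFM and not a count model, and 4.2 ties the primary outcome at 36 weeks PMA to FFM. Sections 2.1 and 2.2 rank the hypotheses outright. This is good evidence of intent and supports the remedy below. It does not remove the conflict, because 3.2.7 and the Abstract still place the microbiome under the primary heading and nothing states the domain reading.

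Two stronger readings are tempting, and the documents support neither.

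- *The trial has neither 5% error nor 80% power for its central hypothesis.* With one test per outcome, these failures belong to different success rules. Accepting either outcome raises error but does not reduce the chance of a positive result. Requiring both holds error and reduces power. FFM alone has neither problem.
- *Joint power is 64%, from 0.80 × 0.80.* The second 0.80 is power to detect a single taxon at about a 2-fold effect, not power for composition or diversity, and the product also assumes independence. In addition, the word *and* in the central hypothesis is not a stated decision rule: 2.1 and 2.2 split that hypothesis into two, and no section requires joint success.

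**Conclusion.** The concern holds as an unresolved conflict of ranking with no success rule. It should be corrected, but it does not undermine the trial's sizing for FFM.

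The size depends on the rule adopted. Error is up to 9.75% if either of two outcomes can carry a positive claim, or about 7.8% at an assumed correlation of 0.8. It is at most 14.3% if FFM, composition and diversity each count. These upper values rest on independent tests, with correlated tests taken as jointly normal. If both outcomes were required, with one test each, error would be controlled and power would drop by an amount the documents do not allow one to calculate.

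Most of the plan points to FFM as the intended single primary. The correction is therefore mainly one of making the Abstract and 3.2.7 agree with 2.1, 2.2 and 4.2.

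**What to change.** 1. **Abstract and 3.2.7.** Name FFM-for-age Z-score at 36 weeks PMA as the single primary outcome, tested at two-sided 0.05. Move the microbiome to the secondary outcomes (Abstract and 3.2.8).
2. **Abstract, central hypothesis.** Add that it is tested as a primary and a secondary hypothesis (2.1 and 2.2), not by joint success.
3. **4.1.** State that the microbiome is tested confirmatorily only if FFM is significant, and in a fixed order: for example one named diversity index at a named time point, then one named test of overall composition. If an earlier test fails, later ones are descriptive.
4. **4.1, taxon-level models.** Report these as exploratory, or apply false-discovery control.

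Sample size and data collection do not change, whereas an equal alpha split would need about 193 enrolled. The fix has three costs. A microbiome result cannot be presented as a primary finding, and it loses confirmatory status if FFM is not significant. Two global microbiome tests that the plan does not now contain must be specified. The taxon-level models, the only microbiome analyses the plan now models and powers, take a supporting role. The changes should be made before any outcome data are compared by group.

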### 3.2.8. Secondary Outcomes

- PGF, FFM, %FFM, BF and %BF at 36 weeks PMA, growth velocity rate (g/kg/d) between birth and 36 weeks PMA, and anthropometric measures at 36 weeks PMA (weight, head circumference, and length).
- Respiratory support at 36 weeks PMA
- Bronchopulmonary dysplasia (BPD) at 36 weeks PMA

### **3.2.9. Additional Safety Outcomes**

- Death
- NEC stage 2 or 3
- SIP
- Culture-proven sepsis

### **3.2.10. Compliance Monitoring**

Unlike many enteral feeding trials in EPT infants, including our preliminary trial, the primary intervention of this trial will be masked. Masking will reduce problems of compliance with the new intervention and reduce surveillance and ascertainment biases.

### **3.2.11. Study Specimens**

We will obtain written informed consent from the parent(s) to collect stool samples weekly from birth to postnatal day 28 and a stool sample before hospital discharge. We will also obtain consent to collect a serum sample prior to hospital discharge to measure biomarkers of anabolism.

## **3.3. POTENTIAL RISKS AND BENEFITS TO SUBJECTS**

This is non-exempt human subjects research.

### **Risk to Human Subjects**

Human Subjects' Involvement, Characteristics, and Design. In this clinical trial, 150 study participants will be randomly assigned in a 1:1 allocation ratio to receive either a protein-enriched human milk diet (intervention group) or a usual human milk diet (control group) during the first 2 weeks after birth. Patients admitted to the UAB Neonatal Intensive Care Unit between July 2020 and December 2022 will be screened to determine eligibility for the trial. Our study population will reflect the epidemiology of prematurity in the state of Alabama, with approximately 51% being Black (African-American), 47% White (Non-Hispanic Caucasian), and the remaining 2% Hispanic/Other. This study population has been selected based on the frequency of postnatal growth problems observed in extremely preterm infants and the increased risk of adverse health outcomes in this vulnerable population.

Study Procedures, Materials, and Potential Risks. For study participants, data will be collected from electronic medical records. Data containing identifying information will be available only to the PI and research personnel directly involved with this study. Information about the study

will be shared without individual identifiers. Data will be collected from medical records in accordance with the study protocol. This will include demographic data and other nutrition/feeding data. This protocol will be reviewed by the Institutional Review Board of the University of Alabama at Birmingham.

*Potential risks:* The probability of risk for higher frequency of feeding interruptions in a patient that participates in this trial is not different than the probability of higher frequency of feeding interruptions in a patient that does not participate in the trial. Other theoretical risks of this study are related to clinical decompensation during assessment of infant body composition. They include increased risk of bradycardia or desaturations. Previous studies, including ours (unpublished data), have not reported an association between assessment of infant body composition and any of the above-mentioned risks. Similarly, studies of high-protein supplementation in preterm infants, primarily those fed formula did not report tolerance problems or increased risk of metabolic acidosis or high BUNs and it is unlikely that significantly adverse effects will be observed with excessive amounts of protein, particularly if the supplement is of high digestibility. Infants may experience some transient discomfort during the PeaPod® assessment which requires them to wear a tight-fitting cap but no other clothing or blanket. Therefore, there are no known risks associated with this trial except loss of confidentiality, as it involves data collection and imaging recording. This is one of the most common risks of participation in clinical research. Accordingly, our team has designed a strategy to protect participant confidentiality. All participants will be informed of study procedures and gauged for understanding of study tasks. In addition, study personnel will follow regulatory guidelines for obtaining informed consent and manage study data that includes personal information.

*Alternative treatments and procedures:* Participants in the intervention and control groups will have full access to all available standard of care clinical services at our neonatal unit, and parents are permitted to withdraw or refuse participation at any time. Serious adverse events will be reported to the DSMB and to the principal investigator.

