## **Secondary Outcome(s)**

Secondary efficacy outcomes will include postnatal growth failure (PGF), FFM, %FFM, body fat (BF), and %BF at 36 weeks PMA, growth velocity rate (g/kg/d) between birth and 36 weeks PMA, and anthropometric measurements at 36 weeks PMA (weight, head circumference, and length). The primary safety outcomes will include intestinal perforation, NEC stage 2 or greater, culture-proven sepsis, and death.

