### **Potential Benefits of the Proposed Research to Research Participants and Others**

Potential benefits of this study include safety and efficacy data on early life protein-enriched human milk diets as a dietary intervention to prevent nutritional deficits, reduce postnatal growth failure, and increase fat-free mass accretion in preterm infants. Better quantitative and qualitative outcomes of growth may also be associated with improved long-term neurodevelopmental outcomes.

Reductions of postnatal growth failure and improved nutritional parameters could improve long-term neurodevelopmental outcomes of infants who survive to hospital discharge. There will be benefit to the medical community in providing additional information on infant body composition of preterm infants.

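### No safety or secondary outcome measures feeding interruptions, feeding tolerance, metabolic acidosis or raised BUN, so the safety data will not cover risks that the protocol itself raises and sets aside

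*Combined protocol and SAP*

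**What the plan says.** The potential-risks paragraph of section 3.3 deals with feeding and protein risks in two separate statements.

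- **Feeding interruptions.** The sentence begins "The probability of risk for higher frequency of feeding interruptions in a patient that participates in this trial is not different" and makes the comparison with a non-participant. It cites no study.
- **Tolerance, acidosis and BUN.** Earlier high-protein studies are summarised with the words "primarily those fed formula did not report tolerance problems or increased risk of metabolic acidosis or high BUNs". The paragraph then concludes that "it is unlikely that significantly adverse effects will be observed with excessive amounts of protein", particularly with a highly digestible supplement.

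The section on protection against risks goes on to treat complications as no more probable with the enriched diet than with the standard one, and bases the minimal-risk category on that. The benefits section says "Potential benefits of this study include safety and efficacy data on early life protein-enriched human milk diets".

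The outcome lists are short. The abstract says "The primary safety outcomes will include intestinal perforation, NEC stage 2 or greater, culture-proven sepsis, and death". Section 3.2.9 lists the same four events: death, "NEC stage 2 or 3", SIP and "Culture-proven sepsis". Section 3.2.8 covers growth, body composition, respiratory support and "Bronchopulmonary dysplasia (BPD) at 36 weeks PMA".

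**The concern.** The evidence used to discount acidosis and BUN comes mainly from formula-fed infants. The trial population is fed human milk, is extremely immature (section 3.1.1), and receives added protein from feeding day 2 (section 3.2.4). Section 3.1 says the population was chosen partly because feeding problems are frequent at these gestations, yet no feeding outcome is defined.

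If the enriched diet raised BUN, worsened acid-base status or led to more withheld feeds, the planned tables could show no difference on any listed safety outcome, and a reader might take that as reassurance on tolerance. Enteral volume does enter the plan, in section 4.1, but only as a covariate in the adjusted analyses. If the diet reduced intake, that effect would be adjusted for and not reported as a result.

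**Working it through.** **The plan's own figure.** Section 4.2 uses a difference of 0.5, SD 1, two-sided 0.05 and 80% power. The number per group is 2 × (1.96 + 0.84)² × 1² / 0.5² = 62.7, rounded up to 63, or 126 in total. This reproduces the stated 126. It concerns the primary outcome, and the present point does not depend on it.

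**Risks raised against outcomes listed.**

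| Item raised in 3.3 | How it is set aside | Safety outcome (abstract, 3.2.9) | Secondary outcome (3.2.8) |
|---|---|---|---|
| Feeding interruptions | Assertion about trial participation | No | No |
| Tolerance problems | Earlier studies, mainly formula-fed | No | No |
| Metabolic acidosis | Same | No | No |
| High BUN | Same | No | No |

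None of the four appears.

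**Other places where they might be captured.**

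- Section 3.2.11: the only blood sample is one serum sample before discharge, for markers of anabolism. It falls after the exposure of about two weeks.
- Section 3.3 (study procedures): nutrition and feeding data come from the chart, but no variable is defined.
- Section 4.1: volume intake in ml/kg must be extracted, but as a covariate.
- Sections 4.5.1 and 4.5.2: serious adverse events, suspected unexpected serious adverse reactions and concerns raised by caregivers reach the DSMB. None of these is a systematic comparison of laboratory values or withheld feeds by group.

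**Precision for the listed events.** The documents give no event rates, so control rates are assumed. With 75 per group and equal rates p, the 95% half-width for the risk difference is 1.96 × √(2p(1 − p)/75). At p = 0.10 this is 1.96 × √0.0024 = 0.096. The last column gives the intervention-group rate detectable with 80% power (two-sided 0.05, normal approximation).

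| Assumed control rate | Half-width (percentage points) | Detectable rate |
|---|---|---|
| 5% | 7.0 | about 20% |
| 10% | 9.6 | about 28% |
| 20% | 12.8 | about 41% |
| 30% | 14.7 | about 52% |

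An event seen in 0 of 75 infants would have a two-sided 95% upper limit of 1 − 0.025^(1/75) = 4.8%.

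**Precision for an added continuous measure.** In SD units the half-width is 1.96 × √(2/n), and the power for a shift of 0.5 SD is Φ(0.5/√(2/n) − 1.96). The 0.5 SD is borrowed from section 4.2 for illustration.

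- n = 75 per group, a value in every infant: half-width 0.32 SD. 0.5/0.163 = 3.06, and 3.06 − 1.96 = 1.10, so power is about 86%.
- n = 60 per group, assuming 20% without a value: half-width 0.36 SD. 0.5/0.183 = 2.74, and 2.74 − 1.96 = 0.78, so power is about 78%.

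**The case against.** A reader might infer that the trial cannot provide safety data at all. The documents do not support that. NEC, SIP, culture-proven sepsis and death are relevant safety outcomes, analysed by intention to treat with risk ratios and 95% confidence intervals (section 4.1), and the benefits section promises safety data only in general terms.

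A reader might also infer that all four items are presented as harms of protein and dismissed on formula studies. In fact the feeding-interruption sentence concerns participation and rests on no cited study. Acidosis and BUN are mentioned as not increased in earlier work, not as known harms of this diet.

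Nor is the DSMB limited to serious adverse events. It also receives suspected unexpected serious reactions, and any provider or caregiver may write to it about possible harm. Masked caregivers can use that route. It remains case by case and gives no comparison between groups.

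Three further objections have weight:

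- Feeding interruptions may be recoverable from chart data collected anyway. That is true, but without a definition, a time window or a planned comparison the analysis would be post hoc.
- The documents do not say that BUN or bicarbonate is measured routinely in the first two weeks. Testing may follow clinical state, and extreme values become more extreme with more tests. Masking does not remove this if the diet itself changes clinical state. A window ending when standard fortifier is ordered would add a second bias, because that event comes after randomisation and may be delayed by withheld feeds.
- The trial calls itself pragmatic, and the no-greater-complications statement is a rationale for the risk category, not an analysis claim.

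These points limit what the laboratory items can show and determine how the fix must be built. They do not close the gap.

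**Conclusion.** The concern holds as a gap in coverage. None of the four feeding and metabolic risks raised in section 3.3 is measured by a safety or secondary outcome, so the trial will be silent on metabolic and feeding tolerance of added protein and cannot confirm the reassurance in that section. The four listed events remain valid safety outcomes, and the primary analysis and sample size are unaffected.

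The numbers illustrate the size of the gap. The 9.6-point half-width assumes a 10% event rate. The 0.32 SD half-width and 86% power assume a value in all 150 infants, which is a best case. Nothing in the documents shows that the diet causes any of these effects; the point is that the plan would not detect them systematically. The correction should be made, and it is cheap, most clearly for days with feeds withheld.

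**What to change.** Add to section 3.2.9, over a fixed window defined identically in both groups (for example from randomisation to postnatal day 14, which matches the plan's own two-week period):

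1. **Days with feeds withheld**, with a written definition, taken from the feeding data already extracted and reported with days alive in the window so that early deaths are visible.
2. **BUN and bicarbonate or base deficit**, where routine-care values exist. Give a summary that is less sensitive to the number of tests (the mean, or the value nearest a fixed day) alongside the extreme value.

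Compare both by randomised group with mean differences and 95% confidence intervals, and include them in the DSMB reports. Report the number of infants with values and the tests per infant by group. State in advance that the laboratory comparisons are descriptive, because testing is unscheduled and may depend on clinical state.

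Reword the potential-risks and protection paragraphs of section 3.3 to say that these risks will be measured. Otherwise, limit the safety claim in the benefits section to NEC, SIP, sepsis and death.

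The cost is a few more chart fields. No extra blood sampling or change in care is proposed. The drawback is that the laboratory data will be incomplete and unscheduled.
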